### SPECIFIC OBJECTIVES

- To compare the tube-related complications of chest tube insertion in patients who have pursestring suture (U-suture placement) at the time of chest tube insertion versus those without pursestring suture placement that are enrolled for Occlusive adhesive-absorbent dressing application at the time of chest tube removal.
- To compare the incidence of early complications after chest tube removal in patients who have purse-string suture re-approximation of thoracostomy wound versus those who have only Occlusive adhesive-absorbent dressing application (Un-reapproximated wound edges)
- To compare the incidence of late wound complication after chest tube removal in patients who have purse-string suture re-approximation of thoracostomy wound versus those who have only Occlusive adhesive-absorbent dressing application (Un-reapproximated wound edges)

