# STUDY VARIABLES AND DEFINITION

The independent variables to be employed for the analysis include:

- Age of the patient
- Sex of the patient
- Presence of specific co-morbidities (Diabetes, Hypertension, Chronic Liver disease, Chronic kidney disease)
- Charleson Comorbidity Index
- History of cigarette smoking and estimated pack years if positive

- Use of steroids and chemotherapeutic agent
- Abnormal Body mass index (Obesity(BMI> 30kg/m^2), Malnutrition(BMI< 18kg/m^2)

The Dependent variables to be employed for the analysis include:

- Presence of severe pain at the chest tube site after chest tube insertion (Average daily pain score after tube insertion > 5 on the Visual Analog Scale and or Numerical Rating Scale)
- Occurrence of tube dislodgement after chest tube insertion
- Occurrence of peri-tubal leakage of fluid after chest tube insertion
- Presence of wound air suck-in after chest tube removal (indicated by presence of air suck-in sound through the wound into the pleural space during quiet and or forced inspiration)
- Occurrence of wound infection after chest tube removal (presence of purulent or offensive wound discharge with or without fever or presence of wound discharge that is microbiologically positive)
- Occurrence of wound dehiscence after chest tube removal
- Occurrence of early (within 7 days) and late pneumothorax (more than 1 week) after chest tube removal confirmed on chest radiography
- Development of raised or elevated thoracostomy wound scars (unsightly scars appearing like hypertrophic scars or keloids) within 3 months of chest tube removal

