At this stage, for patients in whom a purse-string suture has been assigned to be used (Group A), a size 0 polypropylene suture is used in making the horizontal mattress or U-shaped purse string as illustrated in Figure 3 below.

[figure not shown]

FIGURE 3: Illustration of how the purse-string suture is inserted into the thoracostomy wound

To make this horizontal mattress or U-suture placement or purse-string in the thoracostomy wound, the needle of the suture is inserted from point 1, at 1 cm from the wound edge, through the skin and subcutaneous tissue and then exited through point 2, also 1cm from the wound edge. The needle is then re-inserted through the wound about 2cm along the transverse plane which is point 3. The same motion as performed from point 1 to point 2 is done in a reverse pattern from point 3 to point 4. With this, only the free ends of the suture and the part of the suture between point 2 and point 3 lying on the skin surface will be visible while other parts lie within the thoracostomy wound.

This step of U-suture or purse-string placement will be skipped for all patients assigned to Group B. Thereafter, the blunt dissection is continued with the index finger to the level of the parietal pleura which is breached using the tip of the finger or where the pleural is thickened and fibrotic, with the use of the dissecting forceps. The dissecting finger is introduced into the space to assess for pleural adhesions. As indicated above in the exclusion criteria, all patients with pleural adhesions will be excluded from the study. The intrapleural length of the tube will be estimated from the skin incision to the sternal angle. With the aid of the dissecting forceps, this estimated length of the chest tube with blind-ending external part is then advanced apically and posteriorly into the pleural space.

In both groups, the tube is anchored at the anterior and posterior ends of the wound using size 2 silk sutures placed by narrow horizontal mattress suturing or simple interrupted suturing; to secure the chest tube to the chest wall. For patients in Group A, the placed U-suture or purse-string will be knotted once to create air and water tightness (Figure 4) and the loose ends will also be used to anchor the chest tube by tying the loose ends around the chest for a 2 cm length before making a separate knot on the tube to reinforce the previous silk 2 suture anchorages at both wound ends.

[figure not shown]

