assistance. To ensure synchrony, a short count of one to three is done by the lead surgeon and by the count of three, he completes the knotting down to close the wound just as the tube is rapidly pulled out at a single swipe by the assistance upon completion of the count of three. There will be regular rehearsals and practice of these synchronous actions by all those who will be involved with this study as surgeons and assistants. The wound must be closed to air and water tightness but without strangulating the edges. The suture is trimmed, and a sterile dressing applied as before. There will be strict observance of aseptic technique by all involved in this tube removal process. A chest radiograph is done immediately after to check for presence of iatrogenic pneumothorax. The wound dressing will be removed on the third day and subsequent wound care will be determined by the finding at wound review by the principal investigator on this third day. The protocol to follow will be to continue daily povidone iodine wound care if there is evidence of wound infection but to leave the wound open to fresh air and apply povidone iodine topical cream till the suture is removed by day 7, after tube removal. The pain score will be assessed on a continuous basis (everyday till patient is discharged home and at every contact in the outpatient clinic). The patients will be followed up once a month for atleast 3 consecutive months after chest tube removal. Their pain score, wound outcomes and serial chest radiographic check (immediately after tube removal, at one week after tube removal and at every follow up visit in the outpatient clinic), will be done.

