For Group B patients who did not have a purse-string placed during chest tube insertion, the anchor stitches are the cut at the limbs to release it from the skin. The chest tube is checked that it is free of attachments to the skin, the patient is then instructed to make a full inspiratory effort and thereafter arrest expiration. For unconscious patients on ventilator, the intensivist gives a Valsalva manoeuvre of 35 to 40cm H2O to achieve full inspiration and retains that pressure during the tube removal to simulate arrested expiration. Following the model of synchronized action between two surgeons as described above for Group A patients, the lead surgeon applies the Primapore occlusive-adhesive dressing firmly at the count of three immediately after the assistant has pull out the chest tube from the pleural space in brisk but in a measured fashion. The occlusive dressing is retained for a atleast three (3) days to allow the wound to seal before it is either changed or removed depending on the wound condition. This decision will be taken by the principal investigator. The protocol to follow will be to change the dressing if the wound is not completely sealed after 3days but to leave it open to fresh air with topical application of povidone iodine cream. If there is evidence of wound infection, the dressing will be done using 10% povidone iodine solution and a sterile gauze. A chest radiograph is done to assess for the presence of pneumothorax (immediately after chest tube removal, at one week after removal and at every outpatient clinic visit). The patients are followed up for once a month for atleast 3 consecutive months after chest tube removal.

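### Wound dehiscence has no criterion, and early after tube removal it does not mean the same thing in a sutured wound and a wound left un-reapproximated

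*Combined protocol and SAP*

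**What the plan says.** The section on study variables and definition lists eight dependent variables. One is "Occurrence of wound dehiscence after chest tube removal", with nothing after it. Five of the other seven carry some criterion. Wound infection, for example, is defined as "presence of purulent or offensive wound discharge with or without fever or presence of wound discharge that is microbiologically positive". The study proforma records dehiscence as yes or no after tube removal (item 35) and at each of follow-ups 1 to 5. It has no field for whether the wound has sealed.

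The two groups leave tube removal in different wound states by design. For Group A, the procedure for chest tube removal states: "The wound must be closed to air and water tightness but without strangulating the edges". After the day-3 review, an uninfected wound is left uncovered "till the suture is removed by day 7, after tube removal". For Group B, the insertion procedure states: "This step of U-suture or purse-string placement will be skipped for all patients assigned to Group B". The specific objectives describe this group as "those who have only Occlusive adhesive-absorbent dressing application (Un-reapproximated wound edges". The Group B dressing stays on for at least three days so that the wound can seal, and the removal procedure then says: "The protocol to follow will be to change the dressing if the wound is not completely sealed after 3days". It does not say whether such a wound counts as dehisced.

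**The concern.** Dehiscence ordinarily means that closed edges have come apart. That has an obvious meaning in Group A from the moment the purse-string is tied. In Group B there are no apposed edges at that moment, and for some days an open wound is the expected course. The person completing item 35 for a Group B wound that is not yet sealed can tick yes because it is open, or tick no because it was never closed. The plan supports neither choice over the other.

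That person will usually know the group. The trial is open-label, the principal investigator conducts the day-3 review in Group A and takes the day-3 dressing decision in Group B, and no blinded wound assessor is described. Early complications after removal are a specific objective in their own right, and the hypothesis is a general difference in wound and clinical outcomes. A difference in early dehiscence could therefore be reported as a finding about the closure method when it came from how the box was read.

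**Working it through.** The point rests on comparing the text for the two groups. The arithmetic only shows how few ticks would matter.

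**Step 1. What the box can mean at each time.**

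| Time after removal | Group A | Group B | Same question? |
|---|---|---|---|
| Removal to day 3 | Edges closed by suture | Edges apart under the dressing | No |
| Day 3 to about day 7 | Suture still in place | Sealed, or unsealed with the dressing changed | No, unless sealing is recorded |
| Monthly visits | Suture out | Past the period allowed for sealing | Much closer |

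The ambiguity therefore falls mainly on the early box, item 35.

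**Step 2. Is there a figure to reproduce?** No. The documents give no dehiscence rate for either group, and dehiscence plays no part in the sample size, which is built on acute pneumothorax. The only input taken from that section is 71 patients per group. The counts and rates below are assumptions, and all 142 patients are taken as assessed.

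**Step 3. How few ticks matter.** If all *r* events fall in one group of 71 and none in the other, the two-sided Fisher p-value is

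p = 2 × C(71, r) / C(142, r)

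- r = 5 (5/71 = 7.0%): 2 × 0.0291 = 0.058
- r = 6 (6/71 = 8.5%): 2 × 0.0140 = 0.028
- r = 7 (7/71 = 9.9%): 2 × 0.0067 = 0.013

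**Step 4. A range of recording rules.** Suppose 5% of Group A have true edge separation, and the Group B rate depends on how many unsealed wounds are ticked. The chance of p < 0.05 by Fisher's test at 71 per group is:

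| Recorded Group B rate | Chance of p < 0.05 |
|---|---|
| 0% (treated as not applicable) | 14% |
| 5% | 1% |
| 10% | 12% |
| 20% | 73% |
| 30% | 98% |
| 50% | about 100% |

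Fisher's test is a simple yardstick here. The data analysis section names an adjusted Cox model for complications. That does not remove the difficulty, because a wound that was never closed has no clear time at which dehiscence began.

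**The case against.** The strongest reply is that the authors evidently think the term applies to dressing-only wounds. The study summary describes the Group B dressing as a means of closing the wound. The problem statement reports more dehiscence where an occlusive dressing was used without a suture, and the literature review lists dehiscence among the problems of petroleum gauze. The removal procedure has its own term for the expected early state, unsealed, and does not call it a complication. A sensible clinician could read dehiscence as reopening after sealing, which works in both groups. This stands as far as it goes: a workable reading exists. But none of these places states a criterion, and because sealing is not recorded, that reading could not be checked afterwards.

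A reader might go further and infer that dehiscence cannot occur in Group B, or that the two groups cannot be compared on it at any time. The documents do not support that, for the reasons just given and because the monthly visits ask nearly the same question of both groups.

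A reader might also take six ticks out of 71 as an expected size. It is a hypothetical count, and nothing in the documents predicts it. The one dressing-only series the protocol tabulates (312 patients) has no dehiscence row and one serous discharge requiring suture (0.3%), although its definitions are not given. The mirror image, six true separations in Group A against none possible in Group B, would not be purely a labelling effect either, since those would be real complications of the sutured wounds.

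**Conclusion.** The point holds for the early period after tube removal. Dehiscence is undefined, the groups start from different wound states by design, and following the plan exactly allows an early difference to arise from the recording rule. It should be corrected, but it concerns one of eight listed dependent variables, and chiefly its early recording. It does not touch the pneumothorax outcome used for the sample size, and no change in the number of patients follows from it.

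No size can be given from the documents. Under the assumptions shown, five one-sided ticks fall just short of the 5% level and six pass it. The chance of a nominally significant result runs from 1% to nearly 100% depending on how many unsealed Group B wounds are ticked.

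**What to change.** 1. **Early period.** Replace dehiscence with one outcome judged identically in both groups: wound not sealed at the one-week attendance, assessed in Group A after the suture is out, or reopened after being recorded as sealed.
2. **Recording.** Add a sealed yes/no tick to the proforma at the day-3 review, and a brief wound check with the same tick at the one-week radiograph attendance, in both groups. In Group A the day-3 tick describes a wound still held by suture, so the one-week judgement carries the comparison.
3. **Monthly visits.** Define dehiscence as reopening after recorded sealing, or still unsealed.
4. **Later suture closure.** Report it separately and keep it out of the composite, because it is a treatment decision made by staff who know the group.

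The cost is one definition, one tick-box at two contacts, and one short extra wound check in Group B at one week, where the protocol currently specifies only a radiograph. The results will also be less directly comparable with published dehiscence rates.

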# **RESEARCH QUESTIONS**

- What is the difference in the tube-related complication rates after placing a purse-string suture (U suture placement and retention) for thoracostomy wound re-approximation versus non-placement of purse-string at the time of chest tube insertion?
- What is the difference in the early and late complication rates after using a purse-string suture (U suture) for thoracostomy wound re-approximation versus use of only an occlusive adhesiveabsorbent dressing with unreapproximated thoracostomy wound edges; at the time of chest tube removal?
- What is the difference in pain score after using a purse-string suture (U suture) for thoracostomy wound re-approximation versus use of only an occlusive adhesive-absorbent dressing with unreapproximated thoracostomy wound edges; after chest tube removal?
- Is purse-string thoracostomy wound closure associated with more cosmetic complications of thoracostomy scar in the long term than un-reapproximated thoracostomy edges with an occlusive adhesive-absorbent dressing ?

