The common complications encountered with chest tube insertion are malposition and obstruction, either by occlusion or by kinking; ectopic insertion and tension pneumothorax with significant air leak; hence the need to secure the tube properly (17).Large and medium bore chest drain incisions are usually closed by a suture appropriate for a linear incision(7). Various techniques have been described, but a simple technique of anchoring the tube has not been the subject of a controlled trial (9). A purse string or U-suture placement (horizontal mattress suture) is used to aid removal of the chest drain at a

later date and facilitate closure of the defect on removal of the drain while avoiding the occurrence of an iatrogenic pneumothorax (3,16).

For this technique, the chosen suture should be stout, strong and non-absorbable (silk or prolene) to prevent ease of breakage (7). One or two additional simple or horizontal mattress sutures of generous depth should be placed to properly anchor the tube (7). This suture is also thought to prevent air reentry on drain removal as well as aid in chest drain site healing by apposing the edges of the wound (16). The suture is often tied to close the skin wound snugly around the tube to prevent any peri-tubal leak (4). However, this can result in an unsightly scar and tying this suture and retaining the knot for the purpose of achieving air and water tightness of the incision can worsen the painful experience of patients before and after drain removal. In addition, any delay in tube removal often increases the risk that is inherently associated with the retained suture being a foreign body (16). In other to increase the cosmetic appearance of the scar as well as provide an airtight seal to prevent air re-entry, attempts have been made to place an absorbable suture at the time of drain insertion but such methods may be cumbersome and complicated (16). Some centers have reported significant success with achieving airtightness using single barbed absorbable suture material(15).

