Some commercially available dressings which adhere tightly to the skin and then attach to the drain may also be used but they do not replace the need to stitch the drain firmly in place (10). Another common method is to cover the wound with a water impermeant occlusive dressing material like vaseline gauze or adhesive tape, after removing the chest tubes to prevent air entry into the pleura but the cosmetic result may be unreliable with the wound healing by granulation (11).Petroleum-coated gauze as an occlusive seal was used in the past but it is no longer recommended because it leads to integument breakdown, wound infections, pneumothorax and wound dehiscence (2,7).

Other newer techniques for the management of the chest drain wound after tube removal such as a 2layer method with triclosan-coated sutures have been described(2). This method was designed with lots of advantages such as non-requirement of a stitch removal at follow-up, good wound healing with cosmetically-appealing scars; without an increased risk of infection but it has a drawback of being too expensive with requirement of technical expertise limiting its widespread adoption (2,3).

Sutures may not be necessary, after all, for closure of chest drain site as a study reported very minimal complications when sutures were not used(16). The study showed that the rate of acute pneumothorax after removal was 1.2% as opposed to the documented rate of 6%-10.7% for purse-string sutures. Late pneumothorax rate was 0% and only superficial infections occurred with this method which did not result in empyema thoracis as opposed to the documented rate of 1%-25% for purse-string suture use (16,21,22). There was also a reduction of the cost per patient which was not just from avoiding using a suture but also avoiding the cost of removing such a suture afterwards (16).

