# 2) During chest tube insertion

For procedures performed at the patient's bedside, the patient will lie supine or in the cardiac position depending on the diagnosis and clinical condition. The upper limb will be placed under the head for adequate exposure of the safe triangle which is formed by the anterior axillary fold anteriorly, posterior axillary fold posteriorly with the lateral aspect of the sixth rib forming the base. Skin preparation will be done by 10% povidone iodine painting of the anterolateral hemithorax from sternal midline anteriorly to the posterior axillary line and from the clavicle down to the transverse umbilical line. The painting will involve the elbow and finally the axilla will be cleaned. This motion will be carried out thrice to achieve optimal skin sterilization and minimize the risk of contamination.

Thereafter, sterile drapes will be applied to isolate the intercostal space at the mid-axillary line and the surrounding region. The elected site of skin incision is measured using a sterile ruler and marked prior to anaesthesia. Local infiltration of the marked area of skin incision will be done using calculated dose of 2% xylocaine with adrenaline (maximum of 5mg per kg dose). The depth of infiltration should extend to the 5th intercostal space to include the intercostal muscles. After establishing effectiveness of local anaesthesia, a 4cm skin crease incision is then made along the body or lower border of the sixth rib at the mid-axillary line, using a surgical blade and the incision is deepened through the subcutaneous tissue by blunt dissection using a curved number 3 artery forceps or a Kelly forceps. The subcutaneous dissection should create a tunnel extending from the skin incision on the outside to the fifth intercostal space in other to create a superior skin flap. This tunneling is required to create a flap valve-like mechanism aimed at providing an additional method of preventing peritubal leakage after chest tube insertion and development of iatrogenic pneumothorax. The instrument dissection should then be carried through the fifth intercostal space at the upper border of the sixth rib. This is to avoid damage to the subcostal neurovascular structures and also to avoid more pain and haemorrhage.

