#### 5) Follow up and treatment adherence

The patients in both groups will be followed up once every month for atleast three consecutive months assessing for evidence of wound infection, pain control and with chest radiography for evidence of pneumothorax. The wound will also be assessed for development of raised or elevated thoracostomy wound scars (unsightly scars appearing like hypertrophic scars or keloids) within 3 months of chest tube removal.

Patients with wound infection will have 10% povidone iodine daily dressing with institution of antibiotic therapy as per unit protocol. All patients with poor pain control (Pain score greater than 5),

involved with in this study, will have their pain control drug regimen escalated as per unit protocol to achieve better pain control.

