(33) USE OF THERAPEUTIC A	ANTIBIOTICS YES() NO()	
IF YES, INDICATE THE GENE	ERIC TYPE , DOSE, FREQUENCY	AND DURATION IN DAYS
	R CHEST TUBE INSERTION):	,
PNEUMOTHORAX:	YES()	NO ( )
TUBE DISLOGDEMEN		NO ( )

SERIAL NO: .....

EMPYEMA:	YES ( )	NO ( )
WOUND INFECTION:	YES ( )	NO ( )
WOUND DEHISCENCE:	YES ( )	NO ( )
FLUID LEAKAGE:	YES ( )	NO ( )
AIR LEAK:	YES ( )	NO ( )
PAIN:	YES ( )	NO ( )

PAIN SCORE: DAY 1	6AM ( )	6PM( )
DAY 2	6AM ( )	6PM( )
DAY 3	6AM ( )	6PM( )
DAY 4	6AM ( )	6PM( )
DAY 5	6AM ( )	6PM( )
DAY 6	6AM ( )	6PM( )
DAY 7	6AM ( )	6PM( )
DAY 8	6AM ( )	6PM( )
DAY 9	6AM ( )	6PM( )
DAY 10	6AM ( )	6PM( )

# SERIAL NO: .....

(35) COMPLICATIONS (IMMEDIATELY AFTER CHEST TUBE REMOVAL):

PNEUMOTHORAX ON IMMEDIATE POST-TUBE REMOVAL CHEST XRAY: YES ( ) NO ( )

PNEUMOTHORAX ON CHEST XRAY DONE AFTER 1 WEEK:

	YES ( )	NO ( )
EMPYEMA:	YES ( )	NO ( )
WOUND INFECTION:	YES ( )	NO ( )
WOUND DEHISCENCE:	YES ( )	NO ( )
FLUID LEAKAGE:	YES ( )	NO ( )
AIR SUCK-IN THROUGH WOUN	ID:	
	YES ( )	NO ( )
MAJOR PAIN:	YES ( )	NO ( )
PAIN SCORE:		
DAY 1	6AM ( )	6PM()
DAY 2	6AM ( )	6PM()
DAY 3	6AM ( )	6PM()
DAY 4	6AM ( )	6PM()
DAY 5	6AM ( )	6PM()
DAY 6	6AM ( )	6PM()
DAY 7	6AM ( )	6PM()
DAY 8	6AM ( )	6PM()
DAY 9	6AM ( )	6PM()
DAY 10	6AM ( )	6PM( )

### (36) COMPLICATIONS AT FOLLOW-UP 1

PNEUMOTHORAX ON FOLLOW UP CHEST XRAY:

	YES ( )	NO ( )
WOUND INFECTION:	YES ( )	NO ( )
WOUND DEHISCENCE:	YES ( )	NO ( )

SERIAL NO:		
HYPERTROPHIC SCAR:	YES ( )	NO ( )
KELLOID:	YES ( )	NO ( )
WOUND PAIN:	YES ( )	NO ( )
IF YES, PAIN SCORE:		

# COMPLICATIONS AT FOLLOW-UP 2

WOUND INFECTION:	YES ( )	NO ( )
WOUND DEHISCENCE:	YES ( )	NO ( )
HYPERTROPHIC SCAR:	YES ( )	NO ( )
KELLOID:	YES ( )	NO ( )
WOUND PAIN:	YES ( )	NO ( )
IF YES, PAIN SCORE:		
PAIN SCORE:	6AM ( )	6PM ( )

# COMPLICATIONS AT FOLLOW-UP 3

WOUND INFECTION:	YES ( )	NO ( )
WOUND DEHISCENCE:	YES ( )	NO ( )
HYPERTROPHIC SCAR:	YES ( )	NO ( )
KELLOID:	YES ( )	NO ( )
WOUND PAIN:	YES ( )	NO ( )
IF YES, PAIN SCORE:		
PAIN SCORE:	6AM ( )	6PM ( )

# COMPLICATIONS AT FOLLOW-UP 4

WOUND INFECTION:	YES ( )	NO ( )
WOUND DEHISCENCE:	YES ( )	NO ( )
HYPERTROPHIC SCAR:	YES ( )	NO ( )
KELLOID:	YES ( )	NO ( )

SERIAL NO:		
WOUND PAIN:	YES ( )	NO ( )
IF YES, PAIN SCORE:	·	
PAIN SCORE:	6AM ( )	6PM ( )
COMPLICATIONS AT FOLLO	W-UP 5	
WOUND INFECTION:	YES ( )	NO ( )
WOUND DEHISCENCE	E: YES()	NO ( )
HYPERTROPHIC SCAF	R: YES ( )	NO ( )
KELLOID:	YES ( )	NO ( )
WOUND PAIN:	YES ( )	NO ( )
IF YES, PAIN SCORE	:	
PAIN SCORE:	6AM ( )	6PM ( )

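### The fourth research question asks about cosmetic complications in general, but only raised scars are recorded, so a widened or depressed scar counts as no complication in either arm

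*Combined protocol and SAP*

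**What the plan says.** The last item under Research Questions is general in scope: "Is purse-string thoracostomy wound closure associated with more cosmetic complications of thoracostomy scar in the long term" than the dressing.

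Study Variables and Definition lists one cosmetic dependent variable: "Development of raised or elevated thoracostomy wound scars (unsightly scars appearing like hypertrophic scars or keloids) within 3 months of chest tube removal". The follow-up section (item 5 of the procedure details) repeats it: "The wound will also be assessed for development of raised or elevated thoracostomy wound scars". In the Study Proforma, each of the five follow-up pages has a yes/no box for "HYPERTROPHIC SCAR" and another for keloid. There is no field for width, depression, contour, a scar scale or a patient's rating. Wound dehiscence has its own box, but as a wound event.

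Both arms have the same wound: "a 4cm skin crease incision is then made". In Group A the edges are drawn together at tube removal; in Group B they are covered but not re-approximated.

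The literature review says of the purse-string: "However, this can result in an unsightly scar". Of covering the wound with an occlusive material it says "the cosmetic result may be unreliable with the wound healing by granulation".

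**The concern.** The question and the measurement do not cover the same ground. The question asks about cosmetic complications of any kind; the form can detect only scars that stand up from the skin. A patient left with a broad or sunken scar is recorded exactly like a patient with an excellent one.

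This matters more than usual because the two arms heal differently by design. One wound is apposed and the other is not, so the mix of poor scar types may well differ between arms. If it does, an outcome that counts one type and ignores the rest will miss more poor scars in one arm than in the other. The trial would then report a cosmetic comparison whose answer depends partly on which scars were eligible to be counted. Scar appearance that was not recorded at the visit cannot be reliably recovered at analysis.

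**Working it through.** The plan gives no scar rate and no scar-based sample size, so there is no figure to reproduce. The check has two parts.

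**1. The passages side by side**

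| Place | What it covers or predicts |
|---|---|
| Research Questions, fourth | Cosmetic complications of the scar, type not limited |
| Study Variables; follow-up section | Raised scars only |
| Study Proforma, follow-ups 1 to 5 | Hypertrophic scar yes/no; keloid yes/no |
| Literature review, management of the wound | Suture may leave an unsightly scar (shape not stated); healing by granulation under an occlusive cover may look unreliable (shape not stated) |
| Literature review, wound outcomes | Apposed edges heal with less inflammation, less granulation tissue and little contraction |
| Same section, later | Occlusive dressings give a scar that is harder to see and looks better |

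The first three rows establish the gap: non-raised poor scars fall within the question and outside the outcome. The last three show that the background points both ways. A complete scar outcome could test those predictions against each other; a raised-only item cannot.

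**2. How much the gap could matter (all rates assumed)**

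Let r be the proportion with a raised scar and o the proportion with a poor scar that is not raised, with A the suture arm and B the dressing arm. A scar that is both raised and widened is counted under r, so the two categories do not overlap.

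- Difference as now recorded: r_B − r_A
- Difference for any poor scar: (r_B + o_B) − (r_A + o_A)

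Results in percentage points, dressing minus suture:

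| Raised A, B | As recorded | Other 5%, 2% | Other 2%, 5% | Other 2%, 10% | Other 2%, 20% |
|---|---|---|---|---|---|
| 10%, 5% | −5 | −8 | −2 | +3 | +13 |
| 15%, 5% | −10 | −13 | −7 | −2 | +8 |
| 10%, 10% | 0 | −3 | +3 | +8 | +18 |
| 10%, 15% | +5 | +2 | +8 | +13 | +23 |

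Example, first row, fourth result column: (5 + 10) − (10 + 2) = +3.

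The recorded difference can understate the advantage of the dressing, overstate it, or have the opposite sign to the full difference. In the last row it already counts against the dressing.

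For scale, one patient among 71 is 1/71 = 1.4 points, so a 5-point difference is about 0.05 × 71 = 3.6 patients. Precision is low in any case. For 10% against 5% with 71 per arm, two-sided 5%, normal approximation: z = [0.05 − 1.96 × √(2 × 0.075 × 0.925/71)] / √[(0.10 × 0.90 + 0.05 × 0.95)/71] = (0.05 − 0.0866)/0.0440 = −0.83, a power of about 20%.

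**The case against.** A reader might infer that the definition favours the dressing arm by construction: raised scars come from sutures, and wide or sunken ones from wounds left to granulate. The documents do not support this.

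- The item is applied identically in both arms.
- No passage ties raised scars to sutures; the review calls the suture scar unsightly without giving its shape. It also credits the polypropylene suture used in Group A with little tissue reaction and better-looking scars.
- More inflammation and granulation when edges are not apposed leaves raised scars possible in Group B, where they would be counted.
- No passage says Group B scars will be wide or depressed. The warning about granulation concerns petroleum-type gauze or adhesive tape and says only that the result may be unreliable, while a later passage predicts a better scar under occlusive dressings.
- The exclusion of people with a personal or family history of unsightly scars applies to both arms. It probably makes raised scars rarer, but gives no direction.

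All of this stands. It can also be said that the outcome is explicit and prospectively defined, that scars do not drive the sample size, and that a result reported strictly as raised scars would be accurate. That stands too, but the stated question is not about raised scars alone, and nothing in the plan limits its conclusion to them. Finally, at these sample sizes a reversal would usually be one of point estimates, not of significant findings. That limits the consequence without closing the gap.

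**Conclusion.** The concern holds as a mismatch of scope. The raised-scar item is narrower than the fourth research question, and a poor scar that is not raised is counted as no cosmetic complication in either arm. This creates a risk of unequal under-ascertainment between arms that heal by different routes. That the arms will differ in their mix of scar types is a reasonable inference from the background, not something the plan states.

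The direction and size of any imbalance are unknown from the documents. The range in the working rests entirely on assumed rates and shows only that the answer could change or stay the same. A built-in advantage for the dressing is not established.

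The change is worth making before enrolment. This is not the sample-size endpoint, but it is a stated research question that the form as drafted cannot fully answer.

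**What to change.** - In Study Variables and Definition and in the follow-up section, define the cosmetic outcome as an unsightly scar of any type: raised, widened, or depressed or puckered.
- On each follow-up page of the proforma, keep the hypertrophic scar and keloid boxes and add boxes for widened and for depressed or puckered. Mark them tick-all-that-apply, so that a scar that is both raised and widened is recorded as such.
- At the third monthly visit, record maximum scar width in mm in both arms. Analyse it as a continuous measure, so that no cut-off is needed for width itself, and add a line to Data Analysis giving the between-arm difference with a 95% confidence interval.
- Report the any-type outcome as the answer to the fourth research question, with raised scars as a component.

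If the form is not changed, reword the fourth question and its conclusion to cover hypertrophic scars and keloids only.

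The cost is protocol wording, two extra boxes per follow-up page and one ruler measurement at an existing visit. No visit is added and no treatment changes. The downside is a slightly longer form and one more unmasked judgement in an open-label trial.
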